2.1.2.1 Administration Regimen

Subjects will apply treatment once daily for up to 12 weeks to all active lesions identified at Baseline and new lesions that arise during treatment. If the investigator determines all lesions are cleared at a visit, the treatment may stop. If treatment is stopped due to clearance, subjects will continue regularly scheduled visits through Week 24 and study drug will be dispensed in case of lesion recurrence between study visits. Prior to Week 12, if lesions recur or new lesions appear

after the subject has cleared, treatment should be resumed. No further treatment will occur after Week 12.

An increase in the number of MC lesions (with or without inflammatory reaction) during the early treatment period is often observed. It is important to instruct the subject/caregiver to treat the new lesions as well as the existing lesions.

Each dose will consist of berdazimer gel or vehicle gel with hydrogel thoroughly mixed together by the subject or caregiver on a supplied dosing guide and applied to the individual lesions. Periocular lesions will be treated if the lesions are at least 2 cm from the edge of the eye. If a subject has more than 20 MC, a second dose of berdazimer gel or vehicle gel with hydrogel can be prepared to ensure appropriate coverage of all lesions.

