Subjects or their caregivers will apply SB206 10.3% or Vehicle Gel once daily for a minimum of 4 weeks and shall continue unless otherwise instructed by the investigator up to 12 weeks to all lesions identified at Baseline and new treatable lesions that arise during the course of the study. Subjects or their caregivers will continue to treat the area until the next scheduled visit even if the lesion(s) clear. At each in-clinic and remote visit, the investigator will count and record the number of active (raised, treatable) molluscum lesions per body area. Complete clearance should be confirmed by an in-clinic lesion count before treatment is discontinued. If the investigator determines all lesions are cleared at a visit, the investigator may instruct the subject to stop treatment. If treatment is stopped due to clearance, subjects will continue regularly scheduled visits through Week 12/ET and all procedures outside of study drug activities should be continued. If lesions recur or new lesions occur between visits after being stopped due to clearance, the subject or caregiver should re-initiate treatment to the recurring and new lesions. A new kit should be dispensed at Weeks 4 and 8 regardless of lesion count so that treatment can be restarted if lesions are observed between visits. An unscheduled visit is not required for the subject/caregiver to resume treatment. No study treatment is planned to be dispensed after the Week 12 visit.

Remote visits may be performed at Week 4 using remote technology. During the Baseline visit, the subject/caregiver will be instructed on the technology to be used for remote visits. After the initial molluscum lesion count is completed, it will be repeated by the same assessor and the subject/caregiver using the subject/caregiver's electronic device that will be utilized to capture photographs for remote visits. This will provide the subject/caregiver an opportunity to practice with the technology and will allow for the assessor to understand lesion appearance in person compared to through the technology platform.

Subjects will be contacted via phone on Day 2 to collect subject information on early dose reactions. At Weeks 16 and 20, subjects will be contacted via phone to capture information regarding MC recurrence and adverse events (AEs); at Week 24, the subject will be seen at the site for a final study visit to assess scarring, keloid, and MC recurrence.

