Prior to the first application of study drug at Baseline, the investigator will assess the subject’s skin as part of the physical examination, including the presence or absence of individual features of erythema, flaking/scaling, crusting, swelling, vesiculation/pustulation, and erosion/ulceration. At Baseline (30 min. post-dose) and at Week 2 through Week 12 the evaluators will rate LSRs on individual features including erythema, flaking/scaling, crusting, swelling, vesiculation/pustulation, and erosion/ulceration using the LSR Assessment scale (Table 7).

Adverse events will be assessed and collected after the initiation of study drug treatment through the end of the subject’s last visit. Treatment-related adverse events and all serious adverse events will be followed up until resolution or up to one year after last treatment, whichever occurs earlier.

Scar formation (scars/keloids/hypertrophic scars) will be assessed starting at the Week 4 visit through Week 24. The investigator will map locations of the molluscum lesions at Baseline. Additional lesions identified through Week 12 will be added to the map. Using the map as a guidance, the investigator will assess the treated areas for scar/keloid formation. All scars, including keloid/hypertrophic scars, that develop after the Baseline assessment should be captured as AEs and assessed for relatedness to study treatment.

If a subject’s treatment is discontinued by the investigator or the subject because of an AE, that AE should be indicated as the reason for treatment discontinuation. All subjects will be encouraged to remain in the study and to complete all required study visits throughout the 24-week study duration.

A Data Safety Monitoring Board (DSMB) will review all available unblinded safety data (including completed patch testing results). Section 11.2 provides additional details regarding the DSMB.

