### 9.4 Extent of Exposure

Study drug exposure will be summarized for each treatment using the total number of applications, the duration of treatment, and the number of subjects requiring a treatment interruption and modification. Duration of treatment is defined as the last application date minus the first application date plus 1. A subject will be deemed to have a treatment interruption if there is at least 1 dose not applied due to investigator’s instruction and to have a treatment modification if there is at least 1 dose which was modified due to investigator instruction.

Study drug compliance will be summarized and calculated as follows:

Compliance [%] = (Actual applications applied)/(Planned applications) × 100, where

- Actual applications applied = Planned applications – the number of applications not applied by the subject which were not investigator instructed.
- Planned applications = Number of applications (days) planned up to the point of treatment discontinuation or date of Week 12 visit, whichever is later.

This implies that if a subject discontinues treatment prior to Week 12 due to complete clearance, then the number of applications takes this information into account and the subject is not penalized for having complete clearance.

Compliance will be further summarized into 2 groups:

1. Subjects who did not have any interruptions or modifications using the same formula as above, and
2. Subjects with modifications or interruptions. For these subjects, an adjusted compliance will be calculated in the following manner: the actual applications applied will be the same as above but the planned applications will exclude the number of doses which were not applied due to investigator's instruction.

Subjects who do not have any interruptions or modifications will have no doses not applied due to investigator's instruction and no doses modified due to investigator's instruction.

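### SAP 9.4 runs planned applications to the later of treatment stop and Week 12, so after an investigator-instructed early stop, days without treatment count as applied doses

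*SAP*

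**What the plan says.** SAP Section 9.4 defines compliance as actual applications divided by planned applications, times 100.

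- **Planned applications:** "Number of applications (days) planned up to the point of treatment discontinuation or date of Week 12 visit, whichever is later".
- **Actual applications:** not a count of doses. They are planned applications minus "the number of applications not applied by the subject which were not investigator instructed".
- **Stated intent:** if a subject stops before Week 12 for clearance, "then the number of applications takes this information into account and the subject is not penalized for having complete clearance".
- **Adjusted compliance**, for subjects with an interruption or modification: "the actual applications applied will be the same as above but the planned applications will exclude the number of doses which were not applied due"; the reason named there is an instruction from the investigator. One dose withheld on instruction is enough to count as an interruption.

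The Protocol supplies the context. Under Section 4.1, "If the investigator determines all lesions are cleared at a visit, the investigator may instruct the subject to stop treatment", and "All subjects will be encouraged to remain in the study and to complete all required study visits throughout the 24-week study duration". Under Section 2.1.2.1, "No further treatment will occur after Week 12". Section 8.6 takes missed doses from the subject diary, supplemented by source notes such as investigator-directed holds.

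**The concern.** Because dosing ends at Week 12 and subjects who stop treatment stay on visits, the later of the two dates is normally the Week 12 visit. The treatment-discontinuation date then has no effect on the denominator. The SAP's own comment says the count reflects an early stop for clearance, but under this rule it does not.

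After an investigator-instructed stop, the remaining days stay in the denominator and also in the numerator, since only misses that were not instructed are subtracted. Days without treatment become applied doses and dilute any doses the subject missed while on treatment.

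The error could differ between arms. In the two earlier phase 3 studies, adverse events led to study drug discontinuation in 3.0% and 7.2% of SB206 subjects against 0.9% on vehicle in each (Protocol Table 2). Clearance at Week 8 was 15.3% against 10.3%, and 13.9% against 5.9% (Protocol Section 2.1.4.3). A reader who uses the table to judge whether subjects received the treatment under test would see too favourable a picture, somewhat more so on SB206.

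**Working it through.** The documents state no compliance figure, so there is none to reproduce. The check applies the SAP formula directly.

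**Inputs**
- Week 12 visit on Day 85, window Day 80 to 90 (Protocol Section 6.7.7).
- Stops on Day 29 and Day 57, the scheduled Week 4 and Week 8 days.
- One planned application per day from Day 1.
- Self-missed doses (14 or 10), a 14-day hold and a Day 60 restart are illustrative assumptions.

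**Formulas**
- SAP: P = max(stop day, Week 12 day); A = P − misses not investigator-instructed; compliance = 100 × A/P.
- Comparison: the same, with P = min(stop day, Week 12 day).

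**Investigator-instructed stop, later Week 12 visit on Day 85**

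| Stop day | Self-missed | SAP rule | Earlier-date rule | Untreated days credited |
|---|---|---|---|---|
| 29 | 0 | 85/85 = 100% | 29/29 = 100% | 85 − 29 = 56 |
| 29 | 10 | 75/85 = 88.2% | 19/29 = 65.5% | 56 |
| 29 | 14 | 71/85 = 83.5% | 15/29 = 51.7% | 56 |
| 57 | 10 | 75/85 = 88.2% | 47/57 = 82.5% | 85 − 57 = 28 |

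For the Day 29 stop, the credited days range from 80 − 29 = 51 to 90 − 29 = 61 across the visit window. With no missed doses the percentage is the same under both rules. It is distorted only when an early stop and self-missed doses occur together.

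**Adjusted compliance.** If the 56 post-stop days are classed as doses withheld on instruction, the Day 29 stopper with no missed doses scores 85/(85 − 56) = 85/29 = 293%. The same mismatch arises without an early stop: a 14-day hold in a full course gives 85/(85 − 14) = 85/71 = 119.7%.

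**Stop on the subject's own decision, Day 29, no earlier misses**
- Later days recorded as missed: (85 − 56)/85 = 29/85 = 34.1%. Nothing is credited, and on-treatment compliance is understated.
- Diary simply ends: 85/85 = 100%, with 56 days credited.

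**No Week 12 date after the stop:** P is the stop day, and nothing is credited.

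**Rough size by arm**
- Adverse-event stops: the error in the 14-miss example is 83.5 − 51.7 = 31.8 points. If every such discontinuation in the earlier studies had looked like this, mean compliance would rise by 0.030 × 31.8 = 1.0 to 0.072 × 31.8 = 2.3 points on SB206, and by 0.009 × 31.8 = 0.3 on vehicle.
- Clearance stops: the Day 57 example has an error of 5.8 points before rounding. If every subject clear at Week 8 had looked like this, the rise would be 0.153 × 5.8 = 0.9 against 0.103 × 5.8 = 0.6 points in one study, and 0.139 × 5.8 = 0.8 against 0.059 × 5.8 = 0.3 in the other.

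**The case against.** The strongest defence is that the formula does what the SAP wants for clearance: "the subject is not penalized for having complete clearance". Stopping for clearance is investigator-instructed, so the post-stop days are not subtracted. This stands as far as it goes, since both the later and the earlier date avoid a penalty. It does not answer the other half of that sentence, that the number of applications takes the stop into account. Only the earlier date does that.

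A reader might infer three stronger things that the documents do not support.

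- **That everyone who stops early is credited.** Protocol Section 4.1 recognises stops by the investigator or by the subject, and after a subject's own stop the later days are subtracted if recorded as missed. Some stops also leave no gap. For suspected allergic contact dermatitis, Protocol Section 7.2.5 places the Week 12/ET assessments at the time of discontinuation, and SAP Section 7 treats that visit as Week 12 when no Study Exit form carries the same date.
- **That the reported number of applications is wrong.** SAP Section 9.4 lists the total number of applications as a separate exposure summary and does not say that it uses the derived count. The diary records daily doses.
- **That efficacy is affected.** Compliance enters no efficacy model or test, and it is not among the examples of significant deviations in SAP Section 9.5 (a list that is not exhaustive). Treatment duration comes from first and last application dates.

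It is also fair to object that changing one word is not enough. Subjects who clear keep study drug and may restart between visits without being seen (Protocol Section 4.1). The fix has to cover them.

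**Conclusion.** The rule is wrong as written. For investigator-instructed early stops followed by a Week 12 visit, it credits all untreated days as applied: 56 for a Day 29 stop, or 51 to 61 across the visit window. With 14 self-missed doses, compliance is 83.5% where on-treatment compliance is 51.7%. Adjusted compliance can pass 100% if the post-stop days are classed as instructed. For subject-initiated stops the direction depends on how later days are recorded, so the rule cannot be said to overstate compliance for all early stoppers.

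The consequence is modest. It reaches descriptive Table 14.1.3.2 in the Safety Population, and the application total only if programmers derive it from this formula. Under the illustrative assumptions above, arm means move by about 2 points or less from either type of stop. Individual values can be badly wrong. The missed-dose counts are assumptions; the crediting of post-stop days follows from the SAP's definitions.

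**What to change.** In SAP Section 9.4:

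1. End planned applications at the *earlier* of treatment discontinuation and the Week 12 visit, and define discontinuation as the final stop of study drug.
2. For subjects who stop for clearance and later re-initiate, count only the days on which treatment was planned: up to the clearance stop, and from re-initiation to the final stop or Week 12. For example, a stop on Day 29 and a restart on Day 60 continued to Day 85 give 29 + 26 = 55 planned days. Without this clause the 30 days from Day 30 to Day 59 would still be credited.
3. In adjusted compliance, remove investigator-instructed days from the numerator as well as the denominator. Item 1 does not correct the 119.7% result for an ordinary hold.
4. State whether the total number of applications is a diary count or this derived value.

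Subjects who stop for clearance remain unpenalised: 29/29 = 100% with no missed doses. The dates, diary entries and source notes needed are already planned for collection. The cost is a few lines of SAP text and programming before unblinding, and somewhat lower reported compliance for some early stoppers.

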6.8.2 Treatment Modifications, Interruptions, and Discontinuation

If a subject experiences an LSR (AE) for the first time, the investigator must confirm if treatment is needed, if a treatment modification (hold treatment for certain areas) is needed, and/or if a treatment interruption (discontinue treatment in all areas) is needed. If the investigator confirms treatment is needed, the subject can continue study treatment on all areas, hold treatment in certain areas, or interrupt treatment completely, and add non-medicated treatment such as petroleum gel as a concomitant medication. This option can be exercised at any point during the study as needed.

If no concomitant treatment is added, the investigator may choose to withhold study treatment on either specific areas (modification) or all areas (interruption) until the investigator confirms it is appropriate to continue. It is recommended to modify or interrupt treatment for 2-3 days before re-starting the study treatment; the investigator should use their discretion for when to reinstate treatment by discussing the status of the AE with the subject/caregiver to determine if the event is resolved or if continued modification/interruption of study treatment is necessary. The investigator will confirm when reintroduction of study treatment can occur. This option can be exercised at any point during the study as needed.

For more severe AEs, concomitant treatment such as corticosteroids can be added while withholding study treatment on specific areas (modification) or all areas (interruption) until the investigator confirms it is appropriate to continue with the study drug. Similar to the modifications and interruptions above, it is recommended to modify or interrupt treatment for 2-3 days before re-starting the study treatment; the investigator should discuss the status of the AE with the subject/caregiver to determine if the event is resolved or if continued modification/interruption of study treatment is necessary. The investigator will confirm when reintroduction of study treatment can occur. This option can also be exercised at any point during the study as needed.

After the resolution of the first LSR and reinitiation of treatment, if a more severe second LSR occurs, it is appropriate to suspect the cause is allergic contact dermatitis. Study treatment on all areas should be discontinued, and after resolution of the second LSR, patch testing is

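### Adjusted compliance in SAP 9.4 takes investigator-held doses out of the denominator but leaves them in the numerator: it is overstated by H/(P − H) whenever a dose was held, and passes 100% when held doses outnumber self-missed doses

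*SAP*

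**What the plan says.** SAP 9.4 (Extent of Exposure) gives the basic formula as "Compliance [%] = (Actual applications applied)/(Planned applications) × 100". Its two parts are:

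- Numerator: "Actual applications applied = Planned applications – the number of applications not applied by the subject which were not investigator instructed".
- Denominator: "Planned applications = Number of applications (days) planned up to the point of treatment discontinuation or date of Week 12 visit, whichever is later".

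Compliance is then shown separately for two groups. Subjects with no interruption or modification keep the basic formula. For subjects with either, an adjusted value is calculated in which "the actual applications applied will be the same as above but the planned applications will exclude the number of doses which were not applied" because the investigator said so.

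Membership of the second group is defined earlier in the same section. "A subject will be deemed to have a treatment interruption if there is at least 1 dose not applied due to" the investigator's instruction. A subject has a "treatment modification if there is at least 1 dose which was modified due to investigator instruction". The section states no upper limit for either version of compliance.

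**The concern.** The basic numerator subtracts only "the number of applications not applied by the subject which were not investigator instructed". A dose held by the investigator is therefore credited as if it had been applied, and the basic formula already forgives holds. The adjusted formula forgives them again by shrinking the denominator, but does not take the credited doses back out of the numerator. Numerator and denominator then count different sets of doses, so the ratio is no longer a proportion and can exceed 100%.

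At stake is whether the compliance figure can be trusted in the subgroup for which the adjustment was added. Holds follow local skin reactions and intolerability, so they may be more frequent on SB206, and the overstatement could then fall unevenly on the two arms.

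**Working it through.** The SAP states no compliance figure, so there is nothing to reproduce. The check evaluates its formulas.

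**Inputs**

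- P, planned applications (SAP 9.4). P = 84 is an assumption for once-daily dosing over 12 weeks; P = 85 is the alternative.
- S, doses missed without instruction. The documents give no figure; values from 0 to 20 were tried.
- H, doses not applied on investigator instruction. Protocol 6.8.2 says: "It is recommended to modify or interrupt treatment for 2-3 days before re-starting the study treatment", so H = 2 or 3 is the documented case. H = 7 and H = 14 are illustrative. The 2-week limit in Protocol 7.2.3 applies to topical corticosteroid use, not to the length of a hold.

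**Formulas**

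1. Basic: (P − S)/P.
2. Adjusted, as written: (P − S)/(P − H).
3. Adjusted, with held doses removed from both parts: (P − H − S)/(P − H).

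**Algebra**

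- Formula 2 minus formula 3 is [(P − S) − (P − H − S)]/(P − H) = H/(P − H). It does not depend on S, is positive whenever H ≥ 1, and is zero when H = 0.
- Formula 2 exceeds 100% exactly when P − S > P − H, that is, when H > S.
- Formula 3 equals 1 − S/(P − H). It cannot exceed 100%, and it is never above the basic value 1 − S/P. Formula 2 is above the basic value whenever H ≥ 1 (and S < P), so the adjustment as written moves the figure in the opposite direction from a consistent one.

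**Numbers, P = 84**

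| H | S | Basic | Adjusted as written | Held doses out of both | Difference (points) |
|---|---|---|---|---|---|
| 0 | 5 | 79/84 = 94.0% | 79/84 = 94.0% | 79/84 = 94.0% | 0 |
| 2 | 0 | 84/84 = 100.0% | 84/82 = 102.4% | 82/82 = 100.0% | 2.4 |
| 3 | 0 | 84/84 = 100.0% | 84/81 = 103.7% | 81/81 = 100.0% | 3.7 |
| 3 | 3 | 81/84 = 96.4% | 81/81 = 100.0% | 78/81 = 96.3% | 3.7 |
| 3 | 5 | 79/84 = 94.0% | 79/81 = 97.5% | 76/81 = 93.8% | 3.7 |
| 7 | 0 | 84/84 = 100.0% | 84/77 = 109.1% | 77/77 = 100.0% | 9.1 |
| 7 | 8 | 76/84 = 90.5% | 76/77 = 98.7% | 69/77 = 89.6% | 9.1 |
| 14 | 0 | 84/84 = 100.0% | 84/70 = 120.0% | 70/70 = 100.0% | 20.0 |
| 14 | 5 | 79/84 = 94.0% | 79/70 = 112.9% | 65/70 = 92.9% | 20.0 |
| 14 | 20 | 64/84 = 76.2% | 64/70 = 91.4% | 50/70 = 71.4% | 20.0 |

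With P = 85 the differences are 2/83 = 2.4, 3/82 = 3.7, 7/78 = 9.0 and 14/71 = 19.7 points.

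**The case against.** The best defence is a second reading. The numerator is itself defined through planned applications. If the adjusted numerator is that same formula, recalculated after held doses have been taken out of the planned count, the result is (P − H − S)/(P − H), which is correct. The wording does not exclude this. It fits less well, because the sentence says the actual applications stay as they were and sets that against a change in the planned applications, and nothing elsewhere in the SAP corrects or caps the value. Even if the second reading was intended, the text admits two values for one subject, while SAP Appendix B requires two independently programmed datasets to agree completely.

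The second objection is that little depends on the figure, and this stands. The overall compliance formula is unaffected and cannot exceed 100%. The primary analysis uses the ITT population (SAP 10) and does not use compliance. The examples of significant deviations in SAP 9.5 do not include compliance, although that list is open-ended. Total applications, treatment duration and the number of subjects with interruptions or modifications are summarised separately, so the underlying information remains visible.

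A reader might also infer that the table is bound to flatter SB206. The documents do not establish that. In the two earlier phase 3 trials, treatment-related TEAEs were 36.6% on SB206 against 16.4% on vehicle, and 36.3% against 6.8% (Protocol 2.1.4.2, Table 2). That makes more holds on SB206 plausible, but these are not hold rates, and no hold rates by arm are given.

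**Conclusion.** The formula is wrong on its natural reading. It overstates adjusted compliance by H/(P − H) for every subject with at least one held dose. At the recommended 2-3 day pause, and assuming P = 84, that is 2.4 to 3.7 points; larger figures depend on hold lengths chosen for illustration.

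It would be tempting to conclude that every subject with a hold will show more than 100%. That does not follow. The value passes 100% only when held doses outnumber self-missed doses; with a 3-day hold and 5 missed doses it is 97.5%, too high but not impossible. Subjects who are in the group only because a dose was modified, with none withheld, get the basic value.

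The consequence is confined to a descriptive summary (Table 14.1.3.2) and a listing (16.2.5.4). No planned efficacy or safety test uses the figure. An uneven effect between arms is an inference, not a documented fact.

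**What to change.** In SAP 9.4, replace the text for subjects with modifications or interruptions by an explicit formula:

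Adjusted compliance [%] = (planned − held − missed)/(planned − held) × 100,

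where held means doses not applied on the investigator's instruction and missed means doses not applied without such instruction. Held doses then leave both parts of the ratio, and the result cannot exceed 100%.

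The cost is one formula in the SAP and the matching derivation in the dataset specification. SAP 9.4 already distinguishes the two kinds of unapplied dose, and Protocol 8.6 takes missed doses from the diary and investigator-instructed changes from the source records, so no new data are needed.
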